### Urine protein-to-creatinine ratio

At Visit 1 (Screening), Visit 2 (Randomization) and Visit 6 (EOT), urine samples will be collected and sent to the central laboratory for protein and creatinine measures, and determination of the protein-to-creatinine ratio.

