### Laboratory abnormalities

Laboratory values below or above the normal range will be graded at three levels (H, HH, HHH for values above normal range and L, LL, LLL for values below the normal range) where L stands for "low", H for "high".

The term "marked abnormality" describes laboratory values above or below the thresholds, with grading of abnormalities at two levels: LL/HH and LLL/HHH. These thresholds have been defined by the sponsor in order to flag and/or communicate abnormal laboratory results from the central laboratory to the investigators, and for the purpose of standardized data analysis and reporting by the sponsor. The definitions of marked abnormal values are based mainly on the Common Terminology Criteria for Adverse Events (CTCAE) grading system (2010 v4.03) and, in specific cases (e.g., lymphocyte levels), are adjusted based on the known PD effect of the study drugs (e.g., LLL threshold for lymphocytes) [CTCAE 2010].

The term ALERT here corresponds to protocol-defined test result threshold requiring an action from the investigator as described in the protocol (e.g., repeat the test; interrupt or discontinue the study drug) and should not be confused with the term "call alert" used by the central laboratory for laboratory results, which will be communicated to the investigator. Not all ALERTS listed in this table will be "call alerts" from the central laboratory and vice versa.

PLEASE NOTE: Thresholds for abnormality of level L or H are not provided in this appendix but will be provided in the laboratory manual. Parameters for which no threshold is defined in [Table 5](#) below may be defined in the central laboratory manual.

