**Table 5**      **Thresholds for marked laboratory abnormalities for ACT-334441**

Parameter	LL	LLL	HH	HHH
Hemoglobin	< 100 g/L (< 10g/dL; < 6.2 mmol/L)	< 80 g/L (<8g/dL; < 4.9 mmol/L)	Increase in > 20 g/L above ULN or above baseline (if baseline is above ULN)	Increase in > 40 g/L above ULN or above baseline (if baseline is above ULN)
MCH	ND	ND	ND	ND
MCV	ND	ND	ND	ND
MCHC	ND	ND	ND	ND
Hematocrit	< 28% (female) < 32% (male)	< 20%	> 60% (male) > 55% (female)	> 65%
Platelet count	< 75 × 10 e9 /L (< 75,000/mm  )	< 50.0 × 10 e9 /L (<50,000/mm  )	> 600 × 10 e9 /L	> 999 × 10 e9 /L
RBC count	ND	ND	ND	ND
WBC count	ND	< 1.9 × 10 e9 /L	> 20.0 × 10 e9 /L (>20 000/mm  )	CTCAE (grade 3) > 100.0 × 10 e9 /L (>100 000/mm  )
Lymphocyte	ND	< 0.2 × 10 e9 /L (< 200/mm  ) ALERT* < 0.2 × 10 e9 /L (< 200/mm  )	> 4.0 × 10 e9 /L (> 4000/mm  )	≥ 8 × 10 e9 /L (> 8000/mm  )
Neutrophils	< 1.5 × 10 e9 /L (< 1,500/mm  )	< 1.0 × 10 e9 /L (< 1000/mm  )	ND	ND
Eosinophils	ND	ND	> 5.0 × 10 e9 /L or > 5% (> 5000 cells/mm  )	ND
Monocytes	ND	ND	ND	ND
Basophils	ND	ND	ND	ND
Polymorphonuclear leucocyte/Band cells	ND	ND	> 90%	> 95%
AST	ND	ND	≥ 3 ULN (U/L) ALERT ≥ 3 ULN	≥ 5 ULN (U/L) ALERT ≥ 5 ULN ≥ 8 ULN
ALT	ND	ND	≥ 3 ULN (U/L) ALERT ≥ 3 ULN	≥ 5 ULN (U/L) ALERT ≥ 5 ULN ≥ 8 ULN
Total bilirubin	ND	ND	≥ 2 ULN (umol/L) ALERT ≥ 2 ULN combined with ALT or AST ≥ 3 ULN	≥ 5 ULN (umol/L)
Alkaline Phosphatase	ND	ND	> 2.5 ULN (U/L)	> 5 ULN (U/L)

Confidential

INR	ND	ND	≥ 1.5 ULN** or ≥ 1.5 times above baseline if on anticoagulation ALERT ≥ 1.5 combined with ALT or AST ≥ 3 ULN	≥ 2.5 ULN** or ≥ 2.5 times above baseline if on anticoagulation
Activated partial thromboplastin time prolonged (aPTT)	ND	ND	> 1.5 - 2.5 × ULN	> 2.5 × ULN
Lactate dehydrogenase	ND	ND	ND	ND
Creatinine	ND	ND	> 1.5 ULN (umol/L) or > 1.5 × baseline	> 3 ULN (umol/L) or > 3 × baseline
Creatinine Clearance (eGFR)	<60 ml/min/1.73m 	<30 ml/min/1.73m 	ND	ND
Urea	ND	ND	> 2.5 ULN (mmol/L)	> 5 ULN (mmol/L)
Uric acid	ND	ND	> 0.59 mmol/L (>10 mg/dL)	> 0.72 mmol/L (>12 mg/dL)
Proteinuria	ND	ND	≥1.0 g/24h	≥3.5 g/24h
Protein/creatinine ratio	ND	ND	>100 mg/mmol***	>300 mg/mmol***

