Albumin	< 30 (g/L)	< 20 (g/L)	ND	ND
Protein total	ND	ND	ND	ND
C-reactive protein	ND	ND	ND	ND
Glucose (Non-diabetic Fasting)	< 3.0 (mmol/L) (< 55 mg/dL)	< 2.2 (mmol/L) (< 40 mg/dL)	> 8.9 (mmol/L) (> 160 mg/dL)	> 13.9 (mmol/L) (> 250 mg/dL)
Potassium	< 3.2 (mmol/L)	< 3.0 (mmol/L)	> 5.5 (mmol/L)	> 6.0 (mmol/L)
Sodium	ND	< 130 (mmol/L) (< 130 mEq/L)	> 150 (mmol/L) (> 150 mEq/L)	> 155 (mmol/L) (> 155 mEq/L)
Calcium (corrected for albumin)	< 2.0 (mmol/L) (< 8.0 mg/dL)	< 1.75 (mmol/L) (< 7.0 mg/dL)	> 2.9 (mmol/L) (> 11.5 mg/dL)	> 3.1 (mmol/L) (> 15.5 mg/dL)
Chloride	ND	ND	ND	ND
Triglyceride	ND	ND	> 3.42 (mmol/L)	> 11.4 (mmol/L)
Cholesterol	ND	ND	> 7.75 (mmol/L)	> 12.92 (mmol/L)
Fibrinogen	< 0.75 - 0.5 LLN or 25 - < 50% decrease from baseline	< 0.25 LLN or < 75% decrease from baseline or absolute value < 50 mg/dL	ND	ND
IgG	ND	ND	ND	ND
IgM	ND	ND	ND	ND
IgA	ND	ND	ND	ND

ANA	ND	ND	ND	ND
Anti-dsDNA	ND	ND	ND	ND
C3	ND	ND	ND	ND
C4	ND	ND	ND	ND
Anti-Sm	ND	ND	ND	ND
Antiribosomal P	ND	ND	ND	ND
Anti-cardiolipin IgA	ND	ND	ND	ND
Anti-cardiolipin IgG	ND	ND	ND	ND
Anti-cardiolipin IgM	ND	ND	ND	ND
Serum pregnancy test	ND	ND	ND	Positive ALERT: Positive

ALT = alanine aminotransferase; ANA = anti-nuclear antibodies; anti-dsDNA = anti-double-stranded DNA; anti-Sm = anti-Smith; aPTT = activated partial thromboplastin time; AST = aspartate aminotransferase; CTCAE = Common Terminology Criteria for Adverse Events; eGFR = estimated glomerular filtration rate; INR = international normalized ratio; MCH = mean corpuscular hemoglobin; MCHC = Mean corpuscular hemoglobin concentration; MCV = mean corpuscular volume; ND = not defined; RBC = red blood cell; ULN = upper limit of normal; WBC = white blood cell.

\*If lymphocyte count < 800 cells/ $\mu$ l at EOS visit, an alert will be sent.\*\* HH and HHH based on CTCAE 2010 v4.03 [CTCAE 2010]. However, an Alert will be sent when INR  $\geq$  1.5 based on the guidance for monitoring liver test abnormalities from Food and Drug Administration (FDA) [FDA 2009]. \*\*\*Source for protein/creatinine ratio thresholds: <http://www.renal.org/information-resources/the-uk-eckd-guide/proteinuria#sthash.jdT5cPIP.dpbs>.

[figure not shown]

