### 5.8.10 Laboratory

Laboratory test results are transferred from the central laboratory or, if assayed locally, entered in local laboratory eCRF. Assessments are performed at each scheduled visit from Visit 1 (Screening) to Visit 7 (EOS), and at unscheduled visits if required.

The following parameters are assayed:

- **Hematology:** Hemoglobin, hematocrit, platelets, MCH, MCV, MCHC, reticulocytes/erythrocytes, erythrocytes, leukocytes count with differential count (basophils, eosinophils, lymphocytes, neutrophils, monocytes, and basophils/ leukocytes, eosinophils/ leukocytes, lymphocytes/ leukocytes, monocytes/ leukocytes, neutrophils/ leukocytes);
- **Blood chemistry:** Aspartate aminotransferase (AST), alanine aminotransferase (ALT), alkaline phosphatase, total bilirubin (TBL), direct bilirubin, lactate dehydrogenase, creatinine, blood urea nitrogen, urate, glucose, cholesterol, triglycerides, sodium, potassium, chloride, calcium, protein, albumin, creatinine clearance;
- **Coagulation tests:** prothrombin time, INR, activated partial thromboplastin time;
- **Urine protein-to-creatinine ratio** (Visits 1, 2 and 6): Creatinine, protein, protein/ creatinine.

For women of childbearing potential, serum pregnancy tests are performed at Visit 1 (Screening) and Visit 7 (EOS) (central laboratory), and urinary pregnancy tests are performed at all other visits and collected in the dedicated eCRF page.

Urine dipsticks are used to perform the urinalysis at all visits (e.g., pH, glucose, proteins, blood, leukocytes) and the results are recorded in the dedicated eCRF page.

The following endpoints are defined:

- Absolute value and absolute change from baseline in laboratory parameters (hematology, blood chemistry, and urinalysis) at each post-baseline analysis visit up to EOS;
- Treatment-emergent laboratory test abnormalities based on reference ranges (central laboratory) and abnormality thresholds (as defined in appendix 7 of the study protocol and in Section 15.2).

For these abnormalities, additional criteria are defined to characterize the occurrence of treatment-emergent abnormalities during the treatment period in each direction separately (low and high).

Treatment-emergent liver function abnormalities occurring at any time post-baseline are identified according to the following criteria, where a subject is considered to have met the criteria if they have at least one abnormality based on the worst post-baseline value measured (up to EOS):

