| HEMATOLOGY | NEUT      | Neutrophils        | 10e9/L        |     | < 1.0  | < 1.5 | 1.8  | 7.7  | 15.4   | NA  |
| HEMATOLOGY | PLAT      | Platelets          | 10e9/L        |     | < 50.0 | < 75  | 130  | 400  | > 600  | > 999   |
| HEMATOLOGY | RBC       | Erythrocytes       | 10e12/L       |     | NA     | NA    | 3.8  | 5.2  | NA   | NA  |
| HEMATOLOGY | RBC       | Erythrocytes       | 10e12/L       | M   | NA     | NA    | 4.5  | 5.9  | NA   | NA  |
| HEMATOLOGY | WBC       | Leukocytes         | 10e9/L        | F   | < 1.9  | NA    | 4.5  | 11.0 | > 20.0   | > 100.0   |
| HEMATOLOGY | LYM       | Lymphocytes        | 10e9/L        |     | < 0.2  | NA    | 1.00 | 4.80 | > 4.0  | ≥ 8   |
| URINALYSIS | PROT      | Protein            | mg/L          |     | NA     | NA    | 10   | 140  | 1000   | 3500  |
| URINALYSIS | PROTCR T  | Protein/Creatinine | g/mol         |     | NA     | NA    | 1.1  | 12.1 | >100   | >300  |
| URINALYSIS | PROTCR T  | Protein/Creatinine | g/mol         |     | NA     | NA    | 1.7  | 7.7  | >100   | >300  |

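### SAP Table 16 applies 24-hour protein excretion cut-offs to a urine concentration and starts the high lymphocyte grade inside the normal range, so two rows of the descriptive laboratory summaries would be mis-graded

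*SAP*

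**What the plan says.** **Urine protein.** Protocol Appendix 7, Table 5 grades proteinuria as an excretion rate, HH from 1.0 g/24 h and HHH from 3.5 g/24 h, and grades the protein/creatinine ratio separately at > 100 and > 300 mg/mmol. SAP Table 16 (section 15.2.1), titled as an adaptation of that table, has "URINALYSIS | PROT | Protein | mg/L | | NA | NA | 10 | 140 | 1000 | 3500", with no comparison operator on the last two cells. The ratio row reads "Protein/Creatinine | g/mol | | NA | NA | 1.1 | 12.1 | >100 | >300".

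**Samples.** Under the protocol's urine protein-to-creatinine heading (section 7.2.1.2), at Visits 1, 2 and 6 "urine samples will be collected and sent to the central laboratory for protein and creatinine measures". SAP 5.8.10 lists the resulting parameters as "Visits 1, 2 and 6): Creatinine, protein, protein/ creatinine". Neither document schedules a 24-hour collection.

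**Lymphocytes.** Table 16 has "LYM | Lymphocytes | 10e9/L | | < 0.2 | NA | 1.00 | 4.80 | > 4.0 | ≥ 8", the columns running LLL, LL, LO, HI, HH, HHH. The HH cut-off is the protocol's own: "> 4.0 × 10 e9 /L (> 4000/mm 3". Protocol Appendix 7 states the grading principle as "Laboratory values below or above the normal range will be graded at three levels".

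**Use.** SAP 11.2.15 derives the reference range indicator by taking the central laboratory's flag and adding to or changing it according to Table 16. SAP 10.9.4 tabulates treatment-emergent abnormalities by parameter and severity.

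**The concern.** A concentration in a single urine sample depends on how dilute the urine is; an excretion rate does not. Carrying the same digits from g/24 h to mg/L fixes the urine volume at 1 L/day without saying so. The row will then under-grade dilute samples, over-grade concentrated ones, and can disagree with the ratio computed from the same tube.

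The lymphocyte row conflicts with itself: a result can lie within the printed normal range and still carry a grade that the protocol reserves for marked abnormality. Because Table 16 drives the derived grade, both defects would pass into the safety tables if programmed as written. Safety is one of the two main objectives.

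**Working it through.** **Inputs from the documents:** 1.0 and 3.5 g/24 h; 100 and 300 mg/mmol (Protocol Table 5); 1000 and 3500 mg/L; 100 and 300 g/mol; lymphocytes LO 1.00, HI 4.80, HH > 4.0, HHH ≥ 8 (SAP Table 16). I read LO and HI as the limits of the normal range.
**Assumed, since the documents give neither:** urine volume 0.5 to 3.0 L/24 h; urine creatinine 5 and 15 mmol/L.

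**1. Reproduce the SAP cut-offs.** mg/L = (g/24 h × 1000) / (L/24 h). At 1.0 L, 1.0 g gives 1000 and 3.5 g gives 3500, exactly the SAP figures.

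**2. Vary the volume.**

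| L/24 h | 1.0 g/24 h in mg/L | 3.5 g/24 h in mg/L | 1000 mg/L in g/24 h | 3500 mg/L in g/24 h |
|---|---|---|---|---|
| 0.5 | 2000 | 7000 | 0.5 | 1.75 |
| 1.0 | 1000 | 3500 | 1.0 | 3.5 |
| 1.5 | 667 | 2333 | 1.5 | 5.25 |
| 2.0 | 500 | 1750 | 2.0 | 7.0 |
| 3.0 | 333 | 1167 | 3.0 | 10.5 |

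No single mg/L value stands in for either protocol threshold.

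**3. Compare with the ratio row.** 1 mg/mmol = 1 g/mol, so the ratio cut-offs carry over correctly. Ratio (g/mol) = protein (mg/L) / creatinine (mmol/L). The two rows share a cut-off only at 1000/100 = 10 mmol/L for HH and 3500/300 = 11.7 mmol/L for HHH.
- Creatinine 5 mmol/L, protein 600 mg/L: ratio 600/5 = 120, HH; protein row unmarked (600 < 1000).
- Creatinine 15 mmol/L, protein 1200 mg/L: ratio 1200/15 = 80, unmarked; protein row HH.

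**4. Lymphocytes (× 10⁹/L).** Under Table 16 as written, 4.1, 4.5 and 4.8 lie within 1.00 to 4.80 and grade HH. The overlap is 4.80 − 4.0 = 0.8 wide, or 0.8/3.8 = 21% of the width of the normal range (not of patients). Grade H would need a count above 4.80 that is not above 4.0, so it can never occur.

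**5. Calcium (minor).** In Protocol Table 5 three pairs convert at about 4: 8.0/2.0 = 4.0, 7.0/1.75 = 4.0, 11.5/2.9 = 3.97. The HHH pair, "> 3.1 (mmol/L) (> 15.5 mg/dL", gives 15.5/3.1 = 5.0. At a factor of 4, 3.1 mmol/L is 12.4 mg/dL, and 15.5/12.4 = 1.25, a 25% disagreement.

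**The case against.** **Proteinuria is already graded properly in the neighbouring row.** This stands, and it limits the consequence. A reader might infer that the trial would miss proteinuria or renal flare; the documents do not support that. Take 1.5 g/24 h at 2 L/day: 750 mg/L, unmarked on protein. The protocol's pairing of 1.0 g/24 h with 100 mg/mmol implies about 1000/100 = 10 mmol of creatinine a day, so the ratio is about 1500/10 = 150, graded HH. Flare is assessed through the SLEDAI-2K increase of more than 3 and adverse events identified as SLE flares (SAP 4.3.2, 5.8.5.2), and SLEDAI-2K proteinuria starts from the dipstick (Protocol Appendix 6). The row feeds no hypothesis test, stopping rule or Table 5 alert.

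**The SAP did not invent the lymphocyte cut-off.** Correct. A reader might infer a SAP error in > 4.0, but the SAP copied the protocol's value; the clash arises from printing it beside an upper limit of 4.80. SAP 11.2.15 also starts from the laboratory's own flag, so it could be argued that 4.1 to 4.8 would stay ungraded. The text does not settle this, which is itself a reason to correct the cell. Few values are likely to be affected: on the planning figures in Protocol 11.6.1 (mean 2.0, SD 0.45), 4.0 is (4.0 − 2.0)/0.45 = 4.4 SD above the placebo mean.

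**Calcium.** A reader might infer that calcium would be mis-graded in the analysis. It would not: Table 16 uses mmol/L only.

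**The origin of 1000 and 3500 is inferred.** True. It rests on the exact numerical match and the table's title; no other basis is given. That the sample is a spot sample is likewise inferred from the absence of a 24-hour collection.

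**Conclusion.** The point holds as a table error with a limited consequence. As written, the urine protein row applies excretion cut-offs to a concentration. Over an assumed 0.5 to 3.0 L/day, its HH threshold corresponds to anything from 0.5 to 3.0 g/24 h, and it can contradict the ratio row on the same sample. The lymphocyte row marks counts above 4.0 and up to 4.8 that its own range calls normal, contrary to the principle in Protocol Appendix 7. The descriptive abnormality summaries for these two rows would be wrong. The ratio row, the LLL < 0.2 lymphocyte grade and the change-in-count analysis are untouched. The sizes depend on the assumed volumes and creatinine; that the protein cut-offs are not equivalent does not, unless every subject passes 1 L a day.

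**What to change.** - **Urine protein (mg/L), SAP Table 16:** set HH and HHH to NA and grade proteinuria by the protein/creatinine row already present. Protocol 4.4 (criteria 2 and 35) itself names the spot ratio as the equivalent of the 24-hour measure, so no valid grade is lost.
- **Lymphocytes, SAP Table 16:** reconcile the HH cut-off with the 4.80 upper limit so that no value inside the normal range is graded as marked, and state in SAP 11.2.15 which source prevails when the laboratory flag and the table disagree.
- **Calcium, Protocol Table 5 (minor):** reconcile the HHH pair so that both units give one threshold.

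The SAP changes are a few cells and one sentence, recorded in SAP section 4.1 and made before the laboratory dataset is derived. Any change to Protocol Table 5 itself needs a written amendment under Protocol 13.6, which costs more than a cell edit. A unit check of the whole of Table 16 is worth doing in the same pass: the hematocrit rows, for instance, are in L/L but carry cut-offs such as < 20 and > 65 that read as percentages.

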### 15.2.2 Definitions of AEs of special interest, S1P1 compounds (09-Sep-2016)

The definitions for adverse events of special interest are based on systematic approach using Standardized MedDRA Queries (SMQ). The additional relevant term can be added to the search or deleted appropriately providing the rationale for the change. The current proposal is based on MedDRA version 19.0. The following safety areas are addressed by the pre-defined adverse events of special interest:

- **Effect on heart rate and rhythm AESI (including hypotension)**

Effect on heart rate and rhythm AESI are identified by the preferred terms in the following SMQ: **Bradyarrhythmias (incl conduction defects and disorders of sinus node function) (SMQ)**. In addition, to the preferred terms included in Bradyarrhythmias (including conduction defects and disorders of sinus node function (SMQ)), the following preferred terms will be added to the search for AEs addressing effects on heart rate and rhythm: “BRADYCARDIA”, “ELECTROCARDIOGRAM RR INTERVAL PROLONGED”, “HEART RATE DECREASED”, “CHRONOTROPIC INCOMPETENCE”, “PRESYNCOPE”, “SYNCOPE” and “LOSS OF CONSCIOUSNESS”.

The following preferred terms will be added to the search for AEs addressing hypotension: “BLOOD PRESSURE DECREASED”, “BLOOD PRESSURE DIASTOLIC DECREASED”, “BLOOD PRESSURE ORTHOSTATIC DECREASED”, “BLOOD PRESSURE SYSTOLIC DECREASED”, “DIASTOLIC HYPOTENSION”, “MEAN ARTERIAL PRESSURE DECREASED”, “ORTHOSTATIC HYPOTENSION”, “PROCEDURAL HYPOTENSION”, “HYPOTENSION”, “CIRCULATORY COLLAPSE”, “BLOOD PRESSURE FLUCTUATION”, “LABILE BLOOD PRESSURE” and “BLOOD PRESSURE AMBULATORY DECREASED”.

- **Cardiovascular AESI**

Cardiovascular AESI are identified by any preferred term in the following SMQs: **Ischemic heart disease (SMQ) or Cardiomyopathy (SMQ) or Cardiac failure (SMQ)** excluding the preferred term “DYSPNOEA” .

- **Hypertension AESI**

Hypertension AESI are identified by the preferred terms in the following SMQ: **Hypertension (SMQ)**

- **Hepatobiliary disorders / Liver enzyme abnormality AESI**

Hepatobiliary disorders/ Liver enzyme abnormality AESI are identified by the preferred terms in the following SMQ: **Drug related hepatic disorders - comprehensive search (SMQ)** This SMQ is included in the SMQ Hepatic disorder (SMQ) but only the preferred terms included in Drug related hepatic disorders - comprehensive search (SMQ) are included to identify hepatobiliary disorders / Liver enzyme abnormality AESI.

- **Pulmonary AESI**

These AEs are identified by the preferred terms the in the following SMQs: **Asthma/bronchospasm (SMQ)** or **Interstitial lung disease (SMQ)**. The preferred terms “DYSPNOEA AT REST”, “DYSPNOEA” and “DYSPNOEA EXERTIONAL” are added to the search pre-defined by SMQs Asthma/bronchospasm or Interstitial lung disease. SMQs related to respiratory system do not cover the preferred terms on investigations (i.e., AEs based on PFT or chest X Ray or CT scan). Therefore, any preferred term from the MedDRA System Organ Class (SOC) ‘Investigations’ identified by the following high level terms (HLT) are added to the search: **‘Respiratory tract and thoracic histopathology procedures’ (HLT)** or **‘Respiratory tract and thoracic imaging procedures’ (HLT)** and **‘Respiratory and pulmonary function diagnostic procedures’ (HLT)** with the exception of the following preferred terms: ‘CAPNOGRAM NORMAL’, ‘END-TIDAL CO2 NORMAL’, ‘EXPIRATORY RESERVE VOLUME NORMAL’, ‘FORCED EXPIRATORY VOLUME NORMAL’, ‘FORCED VITAL CAPACITY NORMAL’, ‘FUNCTIONAL RESIDUAL CAPACITY NORMAL’, ‘INSPIRATORY CAPACITY NORMAL’, ‘MAXIMAL VOLUNTARY VENTILATION NORMAL’, ‘PEAK EXPIRATORY FLOW RATE NORMAL’, ‘PULMONARY FUNCTION CHALLENGE TEST NORMAL’, ‘PULMONARY FUNCTION TEST NORMAL’, ‘RHINOMANOMETRY NORMAL’, ‘SPIROMETRY NORMAL’, ‘TOTAL LUNG CAPACITY NORMAL’, ‘VITAL CAPACITY NORMAL’.

- **Macular edema AESI**

Macular edema AESI are identified by the following preferred terms: “MACULAR OEDEMA”, “MACULAR HOLE”, “MACULAR PSEUDOHOLE”, “MACULAR RUPTURE”, “MACULAR CYST”, “RETINAL OEDEMA”, “DIABETIC RETINAL OEDEMA”, “CYSTOID MACULAR OEDEMA”, “PAPILLOEDEMA”, and “PSEUDOPAPILLOEDEMA”.

- **Infection AESI**

Infection AESI are identified by the adverse events belonging to the SOC (System Organ Class) **Infections and Infestations (SOC)**, only if reported as **serious or severe**.

- **Herpetic infection AESI**

Herpetic infection AESI are identified by the preferred terms in the following high level terms: **Herpes viral infections (HLT)** and the following preferred term will be added to the search for AEs addressing varicella zoster infection: “ENCEPHALITIS POST VARICELLA”, “HERPES GESTATIONIS”, “HERPES SIMPLEX TEST POSITIVE”, “HUMAN HERPES VIRUS 6 SEROLOGY POSITIVE”, and “HUMAN HERPES VIRUS 8 TEST POSITIVE”.

- **Skin malignancy AESI**

Skin malignancy AESI are identified by the preferred terms in the following SMQs: **Skin neoplasmsm malignant and unspecified (SMQ)** or **Skin premalignant disorders (SMQ)**.

- **Non-skin malignancy AESI**

Non-skin malignancy AESI are identified by the preferred terms in the following SMQ: **Malignant tumours** excluding the preferred terms included in the following SMQs: **Skin neoplasms, malignant and unspecified (SMQ)** or **Skin premalignant disorders (SMQ)**.

- **Stroke AESI**

Stroke AESI are identified by any preferred term in the following SMQ: **Central nervous system haemorrhages and cerebrovascular conditions (SMQ)**. This SMQ consists of 3 following SMQs: Conditions associated with central nervous system haemorrhages and cerebrovascular accidents (SMQ), Haemorrhagic cerebrovascular conditions (SMQ) and Ischaemic cerebrovascular conditions (SMQ).

[figure not shown]
- **Seizure AESI**

[figure not shown]
Seizure AESI are identified by any preferred term in the following SMQ: **Convulsions (SMQ)**.

[figure not shown]
### 15.2.3 SF-36 scoring

#### Recoding items

Scores for each question response are indicated on the questionnaire

## Missing data

For an individual domain where 50% or more of the item questions are non-missing, the average of the non-missing items for that subject in that domain is calculated. This average is then be used to impute the remaining missing item questions of that domain. Note imputation should be based on the final domain score after recalibration / reverse scores of precoded scores. If more than 50% of item questions are missing the domain is recorded as missing. Aggregated scores are computed after the imputation rule has been applied to the component domains, but are set to missing if any domain is missing. Subjects with missing aggregate scores are excluded from analyses and summary statistics.

